maintenance after PCa surgery on obesity-driven PCa biomarkers. Forty men with stage T1 or T2 PCa scheduled to undergo RP will be randomized to receive a weight management program (intervention; n = 20) or standardized education materials (control; n = 20). Our pilot work has established that men awaiting RP are very motivated and embrace the pre-surgical intervention as a means to cope with anxiety by improving their health. We employ a weight loss intervention that emphasizes competition, autonomy, technology, cost savings, and male-specific barriers to change—factors that prior studies have found to be important to successful weight loss interventions among men. We also examine critical QoL factors that could affect the feasibility of the intervention in future trials and clinical practice. Our hypotheses and specific aims are:

1. *To test the impact of weight management on obesity-driven PCa biomarkers taken at baseline, 1 week prior to surgery, surgery and 6 months after surgery.

Hypothesis 1.1: Immune suppressive factors will respond to the intervention with reduced total MDSC (Lin- CD11b+ CD33+) and monocytic MDSC (Lin- CD11b+ CD33+ CD14+ CD15-) counts compared to baseline values and to the control group. **Primary Objective**

Hypothesis 1.2: Participants in the intervention group will have a more favorable chemokine, adipokine, and cytokine profile than the participants in the control group.

2. To evaluate how weight management affects weight loss, body composition, and weight maintenance in overweight and obese men with localized PCa.

Hypothesis 2.1: The intervention will lead to significant weight reduction compared to the control group from baseline to 1 week prior to surgery.

Hypothesis 2.2: The intervention will reduce body fat and maintain lean body mass as measured by Dual Energy X-Ray Absorptiometry (iDXA) scans from baseline to 1 week prior to surgery.

Hypothesis 2.3: The intervention will lead to weight maintenance (<3% regain) 6 months after RP.

3. To test the impact of weight management on QoL in PCa survivors.

Hypothesis 3.1: The intervention will report better urinary function and lower urinary bother compared to control 6 months after RP as measured by the Expanded PCa Index Composite (EPIC) Instrument-26.

Hypothesis 3.2: The intervention will improve sexual function and QoL 6 months after RP as measured by the EPIC-26.

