History of radiation therapy for cancer treatment	"
Taking active cancer treatment	"
Undergoing salvage therapy	"
Castration-resistant PCa	Avoid harm to patients with a poor prognosis or altering their course of treatment
Evidence of metastasis	"
Evidence of biochemical recurrence	"
High risk medical condition (e.g. kidney disease, uncontrolled diabetes, etc.)	"

*If patients do not own a compatible device the study team will loan a device to be returned at the end of the study

AIM 2: Evaluate how weight management affects weight loss, body composition, and weight maintenance in overweight and obese men with localized PCa.

Study Intervention components: The cornerstone of weight management for overweight and obese adults is a comprehensive program, which includes a reduced calorie diet along with exercise and behavior change components.⁵⁴ Our weight management program is designed to help participants lose $\geq 5\%$ of their body weight before their RP and to help them maintain that weight loss after their surgery. This goal can be challenging, yet we find that men scheduled for RP are highly motivated. However, the motivation wanes after surgery. Although our four-component intervention may at first glance seem complicated, our approach is actually very simple as demonstrated by the 90% retention in our pilot study.

Behavior therapy/Coaching: Face-to-face coaching sessions are used to discuss progress, overcome obstacles, make adjustments to the diet and exercise regimen, and learn diet and exercise strategies for cancer survivorship. Before the surgery, the one-on-one coaching sessions occur weekly. After the surgery, 4 coaching sessions are given every 6 weeks in a setting with other study participants, spouses/caregivers, and the coach. Coaches are trained as health educators with credentials as either personal trainers or dietitians working under the supervision of [name] who is also board-certified in oncology nutrition and certified as a personal trainer. Patients and coaches also connect within the app for real-time monitoring and reinforcement. The dashboard on the app shows body weight to reinforce self-efficacy and accountability.

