data unreadable, and unusable if the communication is intercepted or accessed without authorization. The system has a patient-facing user platform and a coach-facing monitoring platform.

Patient-facing user platform (LST AtHome). The patient-facing LST AtHome app runs on any device connected to the internet through either an app or web format. The dashboard clearly shows the participants their energy target, their weight progress, a tally of food groups, and physical activity tracking. Each card on the dashboard opens an applet to manage nutrition, physical activity, body weight, or obtain education (exercise videos, preparing/recovering from RP, recipes). The applets presented to the participant are selected by the study team based on the needs of the participant. LST AtHome captures and reports data, and rewards participants for healthy activity through points and leaderboards.

Coach-facing monitoring platform (LST monitor). The health educator-facing LST Monitor shows body weight, diet, physical activity, and adverse events of all the participants at once to the research team in aggregate. The LST Monitor dashboard shows the research team how each participant is progressing and ranks the participants with the least adherent participants listed first to help identify which participants might need extra support and communication.

Control group. Participants in the control group (n = 20) receive the book, “[name] to Surviving Prostate Cancer” by Patrick C. Walsh and Janet Farrar Worthington as well as the American Institute for Cancer Research booklet, “Heal Well, A Cancer Nutrition Guide” at baseline. Our team will collect the same biomarker, anthropometric, QoL, clinical, and diet recall data from the control group at baseline, 1 week prior to surgery, and 6 months post-operation. The only difference in our interaction with these participants will be the absence of any interventional coaching, technology, or meal replacements.

AIM 3: Test the impact of weight management on QoL in PCa survivors.

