Potential benefits of the proposed research. Prostate cancer is the most common cancer in US men along with the increasing trend toward obesity in the general population. The development of dietary approach to improve outcomes from the surgical treatment of prostate cancer and to better understand how weight control impacts the immune system and inflammatory state will improve the quality of life for cancer survivors. The approach will meet the pressing need to identify weight control interventions for cancer survivors that may improve long-term prognosis and survival. Given the minimal risk to subjects and the potential gain from the study, the risks are considered reasonable.

Adverse event reporting:

Participants will be instructed to report any new or worsening medical condition to their coach or on their weekly self-monitoring logs. Adverse events may be obtained from medical updates taken at baseline, 1 week prior to RP, and 6 months after PCa surgery, weekly participant logs, or spontaneous reports from any source. For all adverse events, an Adverse Event Record Form will be completed that includes a description of the event, a classification of the seriousness, an evaluation of the potential relationship to the intervention, and an assessment of need for change in the informed consent or study activities. Adverse events will be reviewed weekly by the PI and monthly by the study team. Any serious adverse event (SAE) will be investigated immediately and assessed for relevance to the study by the study physicians and

medical monitor. All related and unexpected SAEs will be reported to the KUMC IRB/HSC within 48 hours of the report of the SAE.

Safety Monitoring/Medical Monitor. Serious side effects or other problems during this study will be reported to PI, [name], Co-I, [name], and Medical Monitor, [name], MD.

Medical Monitor: *[name], MD*
Assistant Professor of Urology
[contact]

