An external Medical Monitor will evaluate adverse effects. [name] is a qualified physician, not associated with this particular protocol and not under the supervision of anyone on the research team. [name] will monitor data collection and safety by reviewing the research protocol with emphasis on data integrity and patient safety issues. [name] will monitor any adverse events during the course of the study, make decisions about the continuance of subjects, communicate with the investigators and physicians about adverse events, and assess the responsiveness of corrective actions.

More specifically, the medical monitor will be responsible for reviewing:

- Interim side effect/toxicity data for this trial and proposing corrective actions when the side effects for any treatment are unexpectedly severe. Nonetheless, the PI and study team have primary responsibility for monitoring toxicity. Corrective actions by the medical monitor may include:
 - modifying the treatment
 - early suspension of the trial
 - limiting the participation in the trial to a subset of the original subject population
- Interim analyses of outcome data prepared by the statisticians, with recommendations for change in the study status on the basis of these analyses. These changes may include:
 - early termination of accrual
 - release of results consistent with any sequential stopping rules used in the design of the study
 - increases to the accrual goal
 - major changes to the eligibility criteria for the trial
- The impact of independent scientific investigations (other trials) on the trial being monitored, as well as recommending changes based on those external results.
- Requests for data from sponsoring organizations or any other party. This includes requests for preliminary data for planning ancillary studies. These responsibilities end after the unblinding of the trial, with the medical monitor not involved in further review of the trial. However, the research team may consult the medical monitor on other issues thereafter, such as appropriate action for late toxicities.

The medical monitor will have face-to-face meetings with the research team twice per year. More frequent phone conferences will be held if deemed necessary, for an evaluation of adverse events.

ClinicalTrials.gov

The trial is registered on the ClinicalTrials.gov website. ClinicalTrials.gov Identifier:

NCT03261271

References

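### The adverse event instruction relies on a coach and weekly logs that the plan does not give to control men, so harms are likely to be recorded less completely, or later, in the control arm

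*Combined protocol and SAP*

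**What the plan says.** The Adverse event reporting section opens with the instruction to participants: "Participants will be instructed to report any new or worsening medical condition to their coach or on their weekly self-monitoring logs". It does not say that this applies to one arm only.

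The next sentence lists where events may come from: "Adverse events may be obtained from medical updates taken at baseline, 1 week prior to RP, and 6 months after PCa surgery, weekly participant logs". It closes with an open-ended route that does not depend on arm: "or spontaneous reports from any source". Table 3 (Schedule of Evaluations) marks CTCAE 4.0 at the pre-surgery and post-surgery visits and medical history at every visit, with no split by arm. The Aim 1 design text says that the clinic-visit assessments are the same for everyone.

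For the control arm, the Control group section says: "Our team will collect the same biomarker, anthropometric, QoL, clinical, and diet recall data from the control group at baseline, 1 week prior to surgery". The 6-month visit is included too. Adverse events and logs are not named in that list. It continues: "The only difference in our interaction with these participants will be the absence of any interventional coaching, technology, or meal replacements".

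For the intervention arm, the coaching text says: "Before the surgery, the one-on-one coaching sessions occur weekly". It adds a mid-week telephone check-in and, after surgery, four group sessions six weeks apart. The coach-facing platform displays adverse events.

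The Safety Monitoring/Medical Monitor section has the monitor review interim toxicity data, "proposing corrective actions when the side effects for any treatment are unexpectedly severe".

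**The concern.** Read literally, the instruction gives 20 of the 40 men no usable route. A control man has no coach, and no log is described for him. He can volunteer an event, but the sentence that tells participants where to report names nobody he deals with.

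The two arms are also observed at very different intensity. If an event is more likely to be noted when there is frequent contact, two arms with the same true harm will show different recorded counts. Three things are at stake:

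- **Interpretation.** Men awaiting and recovering from prostatectomy will have background events in either arm. A control count collected in the same way helps to judge which events belong to the programme, and the Adverse Event Record Form asks for that judgement on every event.
- **Timeliness.** The investigator's weekly review can cover only events already reported. The 48-hour limit for related, unexpected serious events runs from the report. A control event that is not volunteered may stay unknown until the next visit.
- **Oversight.** The medical monitor's possible actions include changing the treatment and suspending the trial, on the basis of data whose completeness differs by arm.

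**Working it through.** The plan states no adverse event rate, capture rate or between-arm harms comparison, so there is no figure to reproduce. The check sets the routes side by side, counts contacts, and gives an illustration on assumed values.

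**1. Routes by arm**

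| Route | Intervention | Control |
|---|---|---|
| Coach | Yes | No (Control group section) |
| Weekly self-monitoring logs | Yes | None described (inferred; the logs are not defined elsewhere) |
| Coach-facing platform showing events | Yes | No (technology excluded) |
| Medical updates and CTCAE 4.0 at visits | Yes | Yes |
| Spontaneous report | Yes | Yes, but no recipient is named for him |

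Control share: 20/40 = 50% of the men.

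**2. Scheduled post-baseline contacts at which an event could be volunteered**

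Inputs: pre-surgical programme of 4 to 16 weeks; one coaching session a week; one mid-week call a week; 4 group sessions after surgery; 2 post-baseline clinic visits.

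- Intervention, 4 weeks: 4 + 4 + 4 + 2 = 14.
- Intervention, 16 weeks: 16 + 16 + 4 + 2 = 38.
- Without the calls: 4 + 4 + 2 = 10, to 16 + 4 + 2 = 22.
- Control: 2.

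The text says that the mid-week call goes to all participants. It stands within the coaching component, which control men do not receive, so it is counted for the intervention arm only. Dietary-recall calls occur in both arms, are not named as an adverse event source, and are left out.

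**3. Longest gap for control men**

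The two visits fall one week before and 26 weeks after surgery, so about 1 + 26 = 27 weeks pass between structured enquiries.

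**4. Illustration (assumed values, not from the documents)**

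Recorded events = 20 × true rate × capture probability. With equal true rates, the recorded ratio is the intervention capture divided by the control capture. Take intervention capture as 0.9:

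- control 0.7: 0.9/0.7 = 1.29
- control 0.5: 0.9/0.5 = 1.80
- control 0.3: 0.9/0.3 = 3.00
- equal capture: 1.00

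At an assumed true rate of 50%, each arm has 20 × 0.5 = 10 events. The intervention arm records 9; control records 7, 5 or 3. No arm records more than it truly has, so the apparent excess comes entirely from under-recording in control.

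**The case against.** The strongest reply is that collection is already arm-neutral where it counts. The sentence after the instruction provides medical updates and spontaneous reports, Table 3 schedules CTCAE 4.0 without distinguishing arms, and every man is followed by his surgeon. This stands. A reader might infer that adverse event collection fails in half the trial; the documents do not support that. Only the named reporting route is missing for control men.

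A reader might also infer that harms are over-counted in the intervention arm. That is not supported either: extra contact does not create events. The supportable risk is under-recording in control.

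It is also fair to say that contact is not elicitation. The listed session steps and the description of the mid-week call contain no adverse event question, and the applets described for the patient's app do not include an adverse event screen. The counts above are therefore opportunities to volunteer an event, not times when one is asked about.

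Finally, harms are not an endpoint, no between-arm test or safety table is described, and the monitor's wording reads as severity against expectation rather than as a comparison of rates. This limits the consequence but does not remove it. Relationship to the intervention is still judged for each event, the monitor still sees interim data, and the plan does not acknowledge that ascertainment differs by arm. Unequal contact is inherent in a coaching trial, which is a reason to plan for it.

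**Conclusion.** The point holds in a limited form. The instruction directs every participant to a coach or weekly logs; control men have no coach or app, and no log is described for them. Their harms are collected at two post-baseline visits and by spontaneous report, against 14 to 38 contacts in the intervention arm (10 to 22 without the calls). Events are likely to be under-recorded or recorded late in control, so any view of harms by arm may be tilted against the programme.

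The direction rests on the assumption that more frequent contact brings more events to light. The size is unknown: the ratios of 1.29 to 3.00 only restate assumed capture probabilities. The absence of logs in control is an inference. The primary and secondary efficacy analyses are not affected. This is an inexpensive improvement to safety ascertainment, not a flaw that undermines the trial.

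**What to change.** 1. Keep the coach and log route for the intervention arm. Add a named study contact, for example the study coordinator, to whom men in both arms are told to report any new or worsening condition.
2. At the pre-surgery and 6-month visits already in Table 3, ask the same scripted CTCAE 4.0 question in both arms. Record every event given in answer, whether or not it is already known from another source.
3. Add a source field to the Adverse Event Record Form (visit, study contact, coach, log, platform, other spontaneous report), allowing more than one source.
4. State that any between-arm summary of harms uses events elicited at the common visits, with the remaining events listed separately by arm and source.
5. State that the medical monitor continues to receive all events from all sources.

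The cost is one form field, one script and a few lines of protocol text, with no new visits and no change in sample size. The downside is that events known only from the coach, log or app appear outside the between-arm comparison.
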